Knee Strengthening With Hip vs. Ankle Exercises in Women With Patellofemoral Pain Syndrome

September 25, 2025

1 **Abstract**

2 **Purpose:** This study compared the effects of knee strengthening combined with either hip or ankle
3 joint exercises on dynamic knee valgus (DKV), visual analogue scale (VAS) scores during activity,
4 tendon stiffness, muscle structure, ankle range of motion, and muscle strength in women with anterior
5 knee pain. **Methods:** Forty-five female recreational athletes aged 20–40 with anterior knee pain were
6 randomly assigned to three groups: hip + knee exercises (HK group, n = 15), ankle + knee exercises
7 (AK group, n = 15), and stretching alone (control group, n = 15). The HK and AK groups received
8 supervised telehealth-based exercise sessions (30 minutes/day, 3 times/week for 8 weeks), while the
9 control group received only an educational pamphlet. Assessments were conducted at baseline, 4
10 weeks, and 8 weeks.

11

12 **Key Words:** (1) Dynamic alignment (2) Tele-rehabilitation (3) Pain modulation (4) Muscle strength.

13 **Introduction**

14 Anterior knee pain refers to clinical symptoms of pain around the patella that occur during
15 activities such as squatting, running, and climbing stairs due to increased pressure on the
16 patellofemoral joint. Anterior knee pain is a non-contact knee injury, typically characterized by a
17 gradual onset of pain around the knee joint that is not related to trauma. Additionally, the pain tends to
18 worsen with increased activity, leading to limitations in movement and reduced exercise performance
19 (1, 2). Statistics show that this condition accounts for 25-40% of all knee injuries, with a significantly
20 higher prevalence in women than in men (3). This may be related to anatomical differences,
21 particularly the larger knee valgus angle in women. Additionally, characteristics such as muscle
22 strength and muscle coordination in women may also contribute to greater knee joint instability,
23 further increasing the risk of anterior knee pain, impacting quality of life, and raising healthcare costs
24 (4-6).

25 Treating anterior knee pain is particularly challenging because multiple factors cause it. There is
26 currently no consensus on treatment strategies, but scholars generally agree that the primary causes of
27 anterior knee pain include increased dynamic knee valgus (DKV) angle, weakness in the knee and hip

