28 muscles, and poor landing mechanics (7-9). Although the pain associated with anterior knee pain
29 primarily occurs in the anterior knee, the underlying causes are not limited to the knee joint but also
30 involve the hip and ankle joints. Therefore, treatment strategies need to be multifaceted, such as
31 combining hip and quadriceps strengthening, foot and ankle mobility exercises, movement retraining,

32 and patient education, which together target both proximal and distal factors contributing to
33 patellofemoral pain (10-14).

34 Recent studies have shown that hip muscle control and ankle dorsiflexion range of motion
35 (ROM) influence the DKV angle during weight-bearing activities (15). In the top-down kinetic chain
36 theory, the hip abductor and external rotator muscles eccentrically contract to control hip adduction
37 and internal rotation (16). When these muscles are weak, poor neuromuscular control during
38 weight-bearing activities can lead to increased femoral adduction and internal rotation, increasing the
39 lateral force on the patellofemoral joint (17, 18). This results in excessive load on the patellar tendon
40 and facet joints, which is a key factor in anterior knee pain development (19-21). Numerous studies
41 have demonstrated that weakness in the hip abductor and external rotator muscles can lead to patellar
42 rotation and instability (19, 20). In research by Ferber and colleagues, a three-week hip abduction
43 muscle training program for anterior knee pain patients alleviated knee pain and increased knee
44 stability more quickly than the group that only received knee joint training (22). Furthermore,
45 randomized controlled trials have shown that quadriceps training combined with hip abduction and
46 external rotation muscle training is more effective in reducing knee pain than quadriceps training
47 alone (23, 24). The existing evidence suggests that training both the hip and knee joint muscles is
48 more effective than training the hip muscles alone. Additionally, hip muscle training alone is slightly
49 more effective than knee joint training alone (25). Therefore, studies recommend incorporating hip
50 muscle training into the training programs for anterior knee pain patients (21, 26, 27).

51 On the other hand, in the bottom-up kinetic chain theory (2), ankle dorsiflexion ROM and the
52 strength of the ankle plantar flexor muscles play crucial roles in absorbing ground reaction forces

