53 during landing (28, 29). When ankle dorsiflexion is restricted, patients may compensate for the
54 sagittal plane movement deficiencies by increasing the coronal plane movement (30). In other words,
55 when ankle joint angles are limited, the knee joint may increase the DKV angle as a compensatory
56 strategy, leading to a stiffer landing strategy that increases the knee joint's exposure to greater ground
57 reaction forces during weight-bearing, thereby increasing the risk of anterior knee pain (31, 32). In a
58 proper landing process, the forefoot hits the ground, followed by the eccentric contraction of the
59 plantar flexor muscles to assist in ankle dorsiflexion. Thus, the eccentric contraction capacity of the
60 posterior lower leg muscles also plays a crucial role during weight-bearing (33). In other words,
61 restricted ankle dorsiflexion can affect the entire lower limb kinetic chain, increasing the risk of
62 anterior knee pain.

63 In daily life or sports environments, single-leg landing is a common movement in many jumping
64 activities. During landing, if the ankle dorsiflexion angle is restricted, the forward glide of the tibia is
65 reduced, requiring compensatory hip adduction and internal rotation (34). This movement pattern in a
66 closed kinetic chain leads to dynamic knee valgus, increases friction along the patellar tracking path,
67 reduces the lower limb's shock absorption capacity, and subjects the patellar tendon to greater ground
68 reaction forces, leading to anterior knee pain (35). Therefore, the single-leg landing test (SLL) is
69 often used to assess lower limb dynamic alignment and evaluate the DKV angle. Compared to

70 single-leg squat tests or step-down tests, the SLL better reflects the actual lower limb alignment
71 during athletic movements (36).

72 A literature review reveals that only one study has shown that a single session of ankle joint
73 exercise intervention and relaxation can effectively increase ankle dorsiflexion ROM and reduce
74 DKV (37). However, the cases in that study did not involve anterior knee pain, and the intervention
75 was limited to single-session immediate effect. Currently, there is a lack of high-level evidence in the
76 literature to demonstrate that improving the muscle strength around the hip joint and the mobility of
77 the ankle joint can reduce DKV and thereby alleviate the clinical symptoms of anterior knee pain.

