78 Notably, there is only one study that specifically explores the relationship between ankle joint
79 interventions, DKV, and anterior knee pain, and this study only examines the effects immediately
80 postintervention (31). More importantly, as mentioned earlier, most assessments focus on changes in
81 pain and biomechanics. To date, no studies have investigated the long-term effects of exercise
82 interventions on the structural changes in the hip, knee, and ankle soft tissues or explored the potential
83 mechanisms of recovery.

84 Telemedicine is a simple rehabilitation method that overcomes spatial limitations. Particularly
85 during the COVID-19 pandemic, to reduce the risk of face-to-face transmission, many patients were
86 unable to continue their rehabilitation at hospitals (38). As a result, telemedicine became an
87 alternative solution, allowing patients to continue their rehabilitation. Telemedicine not only
88 effectively reduces treatment costs but also improves patient adherence to treatment (39, 40).
89 Telehealth-delivered physical therapy, including telerehabilitation, has been shown in randomized

90 trials to be as effective as face-to-face care for musculoskeletal conditions—yielding comparable
91 improvements in pain, physical function, and quality of life—while systematic reviews report similar
92 outcomes across a broad range of conditions such as low back pain and knee osteoarthritis (41). These
93 findings demonstrate that physical therapy programs can be effectively and successfully administered
94 via telehealth in musculoskeletal populations (42, 43). Although some literature indicates that
95 telemedicine is effective in alleviating pain and improving knee function in anterior knee pain
96 patients, there is still a lack of high-level evidence to support this, and most studies have focused
97 solely on clinical symptoms (44). Therefore, this study adopted 8 weeks of telemedicine as an
98 intervention strategy to further understand the benefits of combining hip or ankle joint exercises on
99 exercise performance, clinical symptoms, and tissue structure in female patients with anterior knee
100 pain. We hypothesized that 8 weeks of telehealth-based supervised exercise, both the hip and ankle,
101 coupled with knee strengthening, would effectively improve DKV and pain in women with anterior
102 knee pain, and both groups would provide comparable benefits.

103

104 **Methods**

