159 chain muscles, with added hip abductor engagement from the resistance band 3(c) Specifically targets
160 the hip external rotators (gluteus medius, gluteus minimus, piriformis) to improve control of hip
161 rotation and reduce dynamic knee valgus 3(d) A progression of (a) that increases challenge to the hip
162 abductors and lateral stabilizers, requiring greater control at the knee and ankle 3(e) Glute bridge with
163 one leg raised using a resistance band – An advanced form of (b), training unilateral gluteal and core
164 strength, while also engaging hip abductors and extensors for pelvic stabilization 3(f) Isolates
165 the gluteus medius and hip abductors, critical for controlling frontal-plane motion and stabilizing the
166 pelvis during single-leg tasks), and hip abductors (Figure 3). For the AK group, the training goals
167 included strengthening the knee extensors (Figure 2), ankle dorsiflexors (Figure 4(a) Strengthens
168 the ankle plantarflexors (gastrocnemius, soleus), improving calf strength and lower-limb push-off

169 power 4(b) A progression of (a) that further develops plantarflexor strength and enhances ankle
170 stability and balance under unilateral loading 4(c) Increases ankle dorsiflexion ROM by mobilizing
171 the talocrural joint, improving tibial forward glide during weight-bearing 4(d) Strengthens
172 the dorsiflexor muscles (tibialis anterior, extensor digitorum longus), enhancing control of foot
173 clearance during gait and landing 4(e) Stretches the gastrocnemius–soleus complex, improving ankle
174 flexibility and reducing compensatory movement patterns), and plantar flexors (Figure 4), as well as
175 performing ankle joint self-mobilization and stretching exercises (Figure 4). The therapist ensured
176 that the participants were familiar with and correctly performing the exercises before they left. At the
177 end of the session, participants were provided with a home exercise demonstration handout to be
178 performed three times per week for eight weeks. The handout included precautions to take during
179 exercise, guidelines for managing exercise injuries, and a contact number for consultation.

180 Home exercise training was remotely supervised. During the home exercise period, participants
181 engaged in moderate-intensity exercise (rate of perceived exertion, RPE, 12-14) three times per week.
182 Each exercise was performed in two sets, with each set consisting of 10-15 repetitions according to

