183 the training plan, and the total exercise time was approximately 30-45 minutes. The therapist used
184 communication software to supervise participants one-on-one remotely, guided them through the
185 exercises, monitored their RPE, and provided individualized, gradual adjustments as needed. The
186 therapist also corrected participants' posture and movements if necessary and adjusted the length or
187 resistance of the resistance bands to increase or decrease exercise intensity based on the participants'
188 abilities.

189 Participants in the stretching group received a knee exercise handout and were instructed on
190 quadriceps and hamstring stretching exercises at baseline. Unlike the HK and AK groups, no remote
191 supervision, monitoring, or follow-up was conducted for the stretching group. This group functioned
192 as the unsupervised control condition.

193

194 Outcome measures

195 *Primary Outcome (DKV)*

196 The Single Leg Landing Task (SLL) was used to measure the DKV angle during single-leg landing.
197 The participant stood on a 30 cm box and first bent the non-testing leg's knee to approximately 90
198 degrees. After stabilizing, the participant jumped forward with the testing leg to a target 10 cm away
199 from the box, maintaining balance for five seconds upon landing. During the test, the non-testing leg
200 was not allowed to touch the ground, the participant was instructed to keep their eyes looking forward,
201 and both arms were crossed over the chest to minimize the influence of arm movement. The entire
202 sequence was repeated twice, and video recordings were made using a smartphone (45). Image
203 Analysis: Before recording, markers were placed on the midpoint of the knee joint (midpoint of the
204 line connecting the medial and lateral femoral condyles), the midpoint of the ankle joint (midpoint of
205 the line connecting the medial and lateral malleoli), both anterior superior iliac spines (ASIS), and the
206 midpoint of the line connecting the ASIS and the knee joint. A smartphone camera was positioned 2
207 meters in front of the participant to record the video. The video was then analyzed using Kinovea
208 software version 0.8.27 (<https://www.kinovea.org/download.html>) to measure the two-dimensional

209 frontal plane projection angle (FPPA). The knee valgus angle was calculated by subtracting the
210 obtained angle from 180 (the larger the value, the greater the knee valgus angle). The sequence was

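### The contrasts with control measure whole supervised programmes, not the added value of hip or ankle exercise, and any claim that the two programmes are comparable needs an HK–AK confidence interval

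*Combined protocol and SAP*

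**What the plan says.** The arms differ as follows.

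- **HK and AK.** Both receive the knee-extensor exercises of Figure 2. For AK the Interventions section says the goals "included strengthening the knee extensors (Figure 2), ankle dorsiflexors (Figure 4(a) Strengthens" and continues with the ankle work; HK has hip work in its place. Both are supervised remotely by a therapist, one participant at a time, three times a week for 8 weeks.
- **Control.** Participants receive a knee exercise handout and baseline instruction in quadriceps and hamstring stretching. After that, no remote "supervision, monitoring, or follow-up was conducted for the stretching group. This group functioned" as the unsupervised control.
- **Sizes.** Participants were "randomly assigned to three groups: hip + knee exercises (HK group, n = 15), ankle + knee exercises" and stretching alone, 15 per arm. No arm receives knee strengthening alone.

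The objectives are worded at two levels. The Abstract's Purpose is about programmes: "This study compared the effects of knee strengthening combined with either hip or ankle" exercises. The hypothesis at the end of the Introduction is also about programmes. It expects supervised telehealth exercise coupled with knee strengthening to improve dynamic knee valgus (DKV) and "knee pain, and both groups would provide comparable benefits". The sentence just before it, which introduces telemedicine as the strategy, gives the aim as an "intervention strategy to further understand the benefits of combining hip or ankle joint exercises on" performance, symptoms and tissue structure.

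The Statistics section plans a 3 × 3 repeated-measures ANOVA. Simple main effects and Bonferroni comparisons follow if the interaction is significant. Data are to be shown as mean and standard deviation. No confidence interval for a difference between arms is mentioned, and no margin is given for calling two arms comparable.

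**The concern.** The aim sentence can be read as asking what hip or ankle exercise adds to knee strengthening. Other parts of the Introduction encourage that reading. One cites trials in which quadriceps training with hip abduction and "external rotation muscle training is more effective in reducing knee pain than quadriceps training" alone. Another notes a lack of high-level evidence in the "literature to demonstrate that improving the muscle strength around the hip joint and the mobility of" the ankle reduces DKV and symptoms.

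Neither contrast with control answers that question, because each also contains knee strengthening, supervision and the control arm's own stretching. The hypothesised result, with both programmes better than control and about equal to each other, would fit a contribution from both additions or from neither. Under the present wording it could still be reported as a benefit of adding hip or ankle exercise.

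The second half of the hypothesis has a related weakness. Whether HK and AK are comparable depends on HK–AK alone, and the plan offers only a significance test for it, conditional on another test.

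**Working it through.** **The plan's own figure.** Required N is 36 for f = 0.45, alpha 0.05 and power 80%. The correlation is not stated. For the between-groups test with 3 measurements and an assumed correlation of 0.5, the noncentrality is 0.45² × 36 × 3 / (1 + 2 × 0.5) = 10.9 on 2 and 33 df. This gives power 0.814, so 36 reproduces under that assumption. Dropout: 36 / 0.90 = 40, as stated. This calculation concerns an overall test and does not bear on what each contrast identifies.

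**What the contrasts contain.** Score improvement as positive and assume additive effects. Let B be knee strengthening plus supervision minus the effect of control's stretching, H the hip work and A the ankle work.

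- HK–control = B + H
- AK–control = B + A
- HK–AK = H − A

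There are three unknowns and only two independent contrasts, so neither H nor A can be solved for. A larger sample does not change this. B is not trivial by design: planned supervised contact is 3 × 8 = 24 sessions, against none for control after baseline.

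**How far H is bounded.** If B ≥ 0, then H is at most HK–control. If A ≥ 0, then H = (HK–AK) + A is at least HK–AK. With H ≥ 0 as well, and taking error-free contrasts in arbitrary units:

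| HK–control | AK–control | HK–AK | Range of H | Share of HK–control |
|---|---|---|---|---|
| 5 | 5 | 0 | 0 to 5 | 0–100% |
| 5 | 4 | 1 | 1 to 5 | 20–100% |
| 5 | 3 | 2 | 2 to 5 | 40–100% |

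The first row is the hypothesised pattern, and there the contrasts say nothing about H. In the other rows H is above zero, but only because A ≥ 0 was assumed. If ankle work could be harmful, HK–AK = 1 would also fit H = 0 and A = −1.

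**Precision of HK–AK.** With 15 per arm, complete follow-up, one time point and no adjustment, df = 28 and the 95% half-width is t(0.975, 28) × √(2/15) = 2.048 × 0.365 = 0.748 SD. The true difference needed for 80% power is 1.06 SD at two-sided 0.05, or 1.25 SD at 0.05/3 (Bonferroni for three pairs). Adjusting for baseline, which is not planned, would multiply the half-width by √(1 − r²). An assumed r = 0.5 gives 0.648 SD and r = 0.7 gives 0.534 SD.

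**How the claim would be reached.** If the interaction is not significant, the plan provides no post-baseline HK–AK comparison. If it is significant, for instance because control differs from both programmes, HK–AK gets a Bonferroni test and no interval. Either way, comparability would be inferred from a non-significant result.

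**The case against.** The strongest reply is that the design answers the question it asks. The Purpose and hypothesis are about combined programmes, and the hypothesis names supervised telehealth delivery as part of the treatment. The aim sentence, read whole, opens with telemedicine as the strategy, so a programme-level reading is natural. The cited quadriceps-alone comparison is presented as existing evidence, not as this trial's comparator. The lack of supervision in control is stated openly. All of this stands. The aim is ambiguous rather than wrong, and comparing programmes with an unsupervised control is legitimate.

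It can also be said that the precision figures use a single-time-point t-test, which is not the planned ANOVA. That is correct. They indicate scale and do not reproduce the planned test.

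Two stronger readings are tempting, and the documents support neither.

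- **A reader might infer that the trial can never show that hip work adds anything.** That goes too far. A true positive HK–AK would show it if effects are additive and ankle work is not harmful. What fails is the inference when HK–AK is near zero, which is the hypothesised case.
- **A reader might infer that the control arm is invalid, or that the plan already claims an added benefit.** The documents contain no results and no conclusion of that kind, and the programme-level objectives do not need a knee-only arm.

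The Experimental Procedure section says without exception that participants were guided and monitored by a therapist. The Interventions section specifically excludes the stretching group. This is a wording conflict to reconcile and does not show that control was supervised.

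**Conclusion.** The point holds in limited form. HK–control and AK–control are effects of whole supervised programmes against unsupervised stretching. They suit the Purpose and the part of the hypothesis that expects improvement. They do not identify the added value of hip or ankle exercise, and under the hypothesised near-equality of HK and AK the hip share of HK–control is unbounded within 0–100%. That range describes attribution and is not an estimate of bias. It assumes additive effects, none harmful, and contrasts without sampling error.

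Separately, the comparability half of the hypothesis would rest on non-significance, with an uncertainty of about ±0.75 SD (unadjusted, one time point, full follow-up). An observed HK–AK near zero therefore leaves a sizeable difference in either direction open. Severity is minor to moderate: the design stands, and the wording and one reported quantity need to change.

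**What to change.** 1. **Introduction, aim sentence, and conclusions.** State the aim as the effect of the whole supervised programme (knee strengthening with hip or ankle exercise) versus unsupervised stretching, together with hip versus ankle exercise given on the same knee strengthening and supervision. Limit conclusions drawn from the contrasts with control to the whole programme.
2. **Statistics.** Report HK–AK for DKV and for pain with its 95% confidence interval whether or not the interaction is significant, and base any statement that the programmes are comparable on that interval.
3. **Minor.** Reconcile the sentence on therapist guidance and monitoring in Experimental Procedure and Random Grouping with the account of the stretching group in Interventions.

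The cost is a few sentences and one extra interval per outcome from data the trial already collects, with no new arm, visits or staff. The downside is a narrower claim. Much of the text is in the past tense, so the change may be retrospective and should be dated; it narrows what is claimed and does not widen it.

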131 anterior knee pain, and no changes in medication use were reported during the study.

132

133 Experimental Procedure and Random Grouping

134 A single-blinded randomized controlled trial was conducted, in which outcome assessors were
135 blinded to group allocation to reduce the risk of bias. Upon arrival at the research laboratory,
136 participants first performed a simple warm-up (5 minutes of cycling) before immediately undergoing
137 pre-tests. The measurements were conducted in the following order: pain index assessment, patellar
138 tendon stiffness measurement, ultrasound examination, ankle joint ROM measurement, DKV angle
139 measurement, and maximum muscle strength measurement. After completing the pre-test (T0),
140 participants randomly drew a numbered card from an opaque box to determine their group
141 assignment for the subsequent 8-week exercise intervention: Group A (ankle + knee joint exercise
142 group, AK), Group B (hip + knee joint exercise group, HK), or Group C (stretching group). After
143 grouping, participants were immediately instructed on and performed the assigned exercise
144 intervention once. Following three training sessions per week, post-tests (same as pre-tests) were
145 conducted at the 4th week (T1) and the 8th week (T2) (Figure 1). Throughout the exercise training
146 period, participants were guided and monitored by a professionally trained physical therapist.

147

148 Interventions

149 Participants in the hip + knee joint exercise group (HK group) and the ankle + knee joint exercise
150 group (AK group) received one-on-one exercise instruction from a physical therapist with a
151 background in sports medicine. The exercise training goals for the HK group included strengthening
152 the knee extensors (Figure 2(a) Primarily targets the quadriceps (knee extensors), improving knee
153 extension strength and stability 2(b) Also strengthens the quadriceps, with greater isolation of the
154 knee extensors compared to (a), focusing on controlled terminal knee extension 2(c) Works
155 the quadriceps, gluteal muscles, and to some extent the hamstrings, emphasizing closed-chain
156 strengthening and functional loading of the lower limb, while also training postural control), hip
157 external rotators (Figure 3(a) Strengthens the hip abductors (particularly gluteus medius) while
158 promoting pelvic stability during lateral movement 3(b) Activates the gluteus maximus and posterior

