237 weight-bearing activities, this study used a weight-bearing lunge test to measure the active
238 dorsiflexion angle of the ankle during weight-bearing. A measuring tape was placed on the floor, with
239 the participant's heel and second toe aligned with the tape. The participant started with their toes 10
240 cm from the wall, touching the wall with the knee while keeping the heel on the ground. The heel
241 must maintain contact with the floor. If the participant could easily touch the wall or could not reach it,
242 the distance was adjusted by 1 cm increments, gradually adjusting the distance forward or backward
243 according to the participant's ability until they could no longer keep the heel fully in contact with the
244 ground. At the maximum angle, a goniometer was used for measurement, with the fixed arm placed
245 flat on the ground and the movable arm aligned with the line connecting the lateral malleolus and the
246 head of the fibula. The test was repeated twice, and the average value was recorded (51).

247 Maximum Voluntary Isometric Strength: A handheld dynamometer (MicroFET3; Hoggan
248 Scientific LLC, USA) was used to measure the maximum isometric strength of the hip abductors,

249 knee extensors, ankle dorsiflexors, and ankle plantar flexors. Each test was repeated twice, and the
250 average value was recorded (52).

251

252 Statistics

253 The sample size for this experiment was estimated using G*Power and calculated using the priori
254 sample size for Repeated Measures ANOVA. The effect size (ES) was set at $f = 0.45$, with an alpha
255 value of 0.05 and a power of 80%. Based on the above calculations, the required sample size was 36
256 participants. Considering a potential 10% dropout rate, 40 eligible participants were to be recruited.
257 However, to increase the statistical power, the final target was to recruit 45 participants.

258 Data processing and analysis were conducted using SPSS 20.0 for Windows statistical software.
259 The significance level for all data was set at $p < 0.05$, and all numerical data were presented as mean
260 \pm standard deviation. The Shapiro–Wilk test was used to determine the normality of the data
261 distribution. If the data were normally distributed, a two-way ANOVA with repeated measures was
262 used to analyze the 3 group factors (hip + knee group, hip + ankle group, stretching group) \times 3 time

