263 factors (pre-test, week 4, post-test) to first examine the significance of the interaction effect. If the
264 interaction effect was significant, indicating that the group and testing time factors influenced each
265 other, a simple main effect test and Bonferroni post hoc comparisons were performed. A One-way
266 ANOVA analysis was used to compare intra-group differences before the intervention, followed by
267 Bonferroni post hoc comparisons. Training adherence was calculated using the formula: (actual

268 training sessions/24) * 100%. Test-retest reliability was verified using the Intraclass Correlation
269 Coefficient (ICC) to ensure the consistency of all measurements.

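### The planned repeated-measures ANOVA, in its standard form, discards any woman who misses a visit; a mixed model would keep her data and limit a modest possible bias in exercise versus control

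*Combined protocol and SAP*

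**What the plan says.** For normally distributed outcomes the Statistics section specifies "a two-way ANOVA with repeated measures was" applied to three groups by three times (pre-test, week 4, post-test). The sequence is "to first examine the significance of the interaction effect" and, if that is significant, "a simple main effect test and Bonferroni post hoc comparisons were performed".

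On loss, the sample-size paragraph says: "Considering a potential 10% dropout rate, 40 eligible participants were to be recruited". The target was then raised to 45. No analysis population, missed-visit rule, imputation or mixed model is stated.

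The Abstract and the Experimental Procedure section schedule the week-4 and week-8 assessments without limiting them to any arm. Contact in between is unequal. The exercise arms are supervised remotely, one-on-one. For the control arm the Interventions section says: "Unlike the HK and AK groups, no remote" "supervision, monitoring, or follow-up was conducted for the stretching group".

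**The concern.** The plan recruits extra women to cover dropout but does not say how dropout is handled in the analysis. Extra recruitment protects power. It does not keep the arms comparable once some women are excluded.

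Deletion of incomplete cases is inferred from the named method, because the plan states no rule. The risk lies in the exercise-versus-control contrasts. If controls who are worsening leave, the remaining controls look better and the benefit of exercise is understated. If controls who have recovered leave, it is overstated. The comparison of the two exercise arms, which carries the comparable-benefits hypothesis in the Introduction, is not affected by this difference in supervision.

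**Working it through.** **1. The plan's own figures.** Inputs from the Statistics section: f = 0.45, alpha 0.05, power 80%, 3 groups, 3 visits. The within-woman correlation is not given; 0.5 is assumed here.

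- Between-groups form: λ = f²·N·m / (1 + (m − 1)ρ) = 0.2025 × 36 × 3 / 2 = 10.94 on 2 and 33 df, power 0.814. The stated 36 is reproduced.
- The interaction form λ = f²(N − k)(m − 1) = 0.2025 × 33 × 2 = 13.37 also gives 36 (power 0.818).
- Dropout: 36 / 0.9 = 40, as stated.
- Complete cases from 45 at 10% loss: 45 × 0.9 = 40.5, above 36. Loss must exceed 20% (45 × 0.80 = 36) before planned power suffers, so the remaining question is bias.

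**2. Would anyone be missing?** If losses are independent at the plan's 10%, the chance that at least one of 45 women is missing is 1 − 0.9⁴⁵ = 0.991.

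**3. Size of the bias.** The documents give no SD, correlation, loss by arm or dropout mechanism, so all of these are assumptions:

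- unit variance at each visit and equal correlation r between visits (0.5 or 0.7);
- loss in the control arm only, at 11% or 21% (about 2 to 3 of 15 women, or 4–7% of 45);
- log-odds of dropout rising by 1 per SD of worsening from baseline to week 4.

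The bias in the baseline-to-week-8 change contrast comes from 1,000,000 draws per scenario. The standard error is √[2(1 − r) × 2/15], which is 0.365 at r = 0.5 and 0.283 at r = 0.7. Biases are absolute, in SD units.

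| r | Control loss | Completers | Bias / SE | Mixed model, week 4 seen | Mixed model, lost before week 4 |
|---|---|---|---|---|---|
| 0.5 | 11% | 0.051 | 0.14 | ≤ 0.002 | 0.026 |
| 0.5 | 21% | 0.091 | 0.25 | ≤ 0.002 | 0.047 |
| 0.7 | 11% | 0.037 | 0.13 | ≤ 0.002 | 0.025 |
| 0.7 | 21% | 0.071 | 0.25 | ≤ 0.002 | 0.051 |

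The mixed model works when week 4 is seen because that value carries the information that drove the dropout. When it is not seen, about 50–72% of the completer bias remains.

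**4. Effect on testing.** For an ungated 5% test, P(|Z + 0.13| > 1.96) = 0.052 and P(|Z + 0.25| > 1.96) = 0.057. Under the plan's sequence, with 8,000 simulated trials of 15 per arm and no true effect:

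- Interaction test: rejects in 5.9% at r = 0.5 (5.2% without dropout) and 5.7% at r = 0.7 (4.8% without).
- One contrast at 0.05/3 after a significant interaction: 0.85% at r = 0.5 (0.95% without dropout) and 1.06–1.10% at r = 0.7 (0.75% without). The Monte Carlo error of each rate is about √(0.01 × 0.99 / 8000) = 0.11 percentage points.

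**5. Other dropout patterns.**

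- Random dropout: bias at most 0.001 SD.
- 10% loss in every arm: 0.002 SD if the dependence on outcome is the same in all arms; 0.047 (r = 0.5) or 0.036 SD (r = 0.7) if only the controls' dropout is informative.
- 20% of controls and 5% of exercisers lost, with selection on baseline or week-4 change: about 0.06–0.17 SD for completers and about 0 for the mixed model. Selection on baseline reverses the sign.
- Dropout driven only by the week-4 level: 0 for both methods.
- Dropout driven by the unseen week-8 change (20% and 5% loss, r = 0.5): 0.17 SD for completers and 0.12 SD for the mixed model.

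**The case against.** The documents report no missed visit, and much of the text is in the past tense, so retention may have been complete. In that case the point has no effect. This stands, and it is why the point is conditional.

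Less contact does not prove that dropout is related to outcome, and the Experimental Procedure section says in general terms that a therapist guided and monitored participants throughout training. The first part stands: differential dropout is a possibility, not a finding. The second does not, because the Interventions section expressly exempts the stretching arm. The two sentences should be reconciled.

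The effect is small. Gated rejection hardly moves: the fall at r = 0.5 is within simulation noise, and the rise at r = 0.7 is about two Monte Carlo standard errors. This stands. The bias falls on the estimate and its interval rather than on the gated test.

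The remedy is partial. It relies on missing at random, leaves half or more of the bias if leavers go before week 4, and did slightly worse than completers in one scenario where loss depended on the unseen week-8 level. Its interaction test is also not exact in a trial this small: with complete data, an unstructured-covariance F test on 42 df rejects about 5.4%. These limits stand and belong in the report. They do not favour the completer analysis, which drops observed data and depends on a stricter assumption about who is missing.

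**Conclusion.** The concern holds. As named, the analysis would discard the observed data of any woman with a missed visit, and the plan offers no alternative although it allows for dropout. The possible bias in exercise versus control is about 0.04–0.09 SD under the main assumptions. It is larger under heavier or stronger selection and nil with complete, random or arm-balanced loss. Neither its size nor its direction can be fixed from the documents. Power is unaffected at the planned 10% loss. Priority is minor to moderate; the change is worth making because it costs little and does no harm to the estimates if no data are missing.

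**What to change.** Replace the ANOVA with a REML linear mixed model (SPSS MIXED, unstructured covariance, Satterthwaite degrees of freedom):

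- Baseline, week 4 and week 8 are all outcomes, with baseline not also a covariate. Group, visit and group × visit are fixed effects.
- Include every randomised woman with any observed value, in the arm she drew.
- The group × visit test takes the place of the ANOVA interaction test, and the Bonferroni comparisons follow as planned.
- Report week-8 between-group contrasts in change from baseline with 95% confidence intervals.
- Tabulate missing values by arm and visit, and say so if there are none.
- If any woman lacks both week 4 and week 8, add a sensitivity analysis that shifts the missing week-8 values by, for example, plus and minus 0.5 SD (an assumed range). For 2 to 3 of 15 women this moves the arm mean by 2/15 × 0.5 = 0.07 to 3/15 × 0.5 = 0.10 SD.

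The cost is a little more analysis work in the same software, and possibly a rerun if the analysis is already done. Precision gain is negligible (standard error about 1% smaller at most). With complete data the contrasts have the same point estimates as the ANOVA cell means.
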